#### SCHEMA

\*\* Disease Assessment: Day 1 of each cycle

#### LIST OF ABBREVIATIONS AND GLOSSARY OF TERMS

Common abbreviations used in oncology protocols are provided below. Program-specific or protocol-specific abbreviations must be added to this list, and unnecessary abbreviations removed, as applicable. Abbreviations that are retained should not be changed.

| Abbreviation         | Term   |
|----------------------|--|
| 5-HT 3    | 5-hydroxytryptamine 3 serotonin receptor                                     |
| AE                   | adverse event  |
| ALL                  | acute lymphoblastic leukemia   |
| ALP                  | alkaline phosphatase   |
| ALT                  | alanine aminotransferase   |
| AML                  | acute myelogenous leukemia   |
| ANC                  | absolute neutrophil count  |
| API                  | active pharmaceutical ingredient   |
| aPTT                 | activated partial thromboplastin time  |
| Ara-C                | Cytarabine   |
| ASCO                 | American Society of Clinical Oncology  |
| AST                  | aspartate aminotransferase   |
| AUC                  | area under the plasma concentration versus time curve                        |
| AUC 24 hr | area under the plasma concentration versus time curve from zero to 24 hours  |
| AUC inf   | area under the plasma concentration versus time curve from zero to infinity  |
| $AUC_{\tau}$         | area under the plasma concentration versus time curve from zero to next dose |
| BCRP                 | breast cancer resistance protein   |
| βhCG                 | beta-human chorionic gonadotropin  |
| BID                  | bis in die; twice a day  |
| BM                   | bone marrow  |
| BSA                  | body surface area  |
| BUN                  | blood urea nitrogen  |
| BZD                  | Benzodiazepines  |
| CBC                  | complete blood count   |
| CFR                  | Code of Federal Regulations  |
| CL                   | clearance, IV dosing   |
| CL P      | plasma clearance   |
| CL Total  | total clearance  |
| C max     | single-dose maximum (peak) concentration                                     |
| CNS                  | central nervous system   |

#### CONFIDENTIAL

This document is confidential. Do not disclose or use except as authorized.

| Abbreviation    | Term  |
|-----------------|---|
| CO 2 | carbon dioxide  |
| CR              | complete remission  |
| CRM             | continual reassessment method                             |
| CRP             | C-reactive protein  |
| CSF-1R          | colony-stimulating factor 1 receptor                      |
| СТ              | computed tomography                                       |
| $C_{trough}$    | single-dose end of dosing interval (trough) concentration |
| CV              | coefficient of variation                                  |
| СҮР             | cytochrome P 450                               |
| DDI             | drug-drug interaction                                     |
| DLT             | dose-limiting toxicity                                    |
| DME             | drug metabolizing enzymes                                 |
| DNA             | deoxyribonucleic acid                                     |
| ECG             | Electrocardiogram   |
| ECOG            | Eastern Cooperative Oncology Group                        |
| eCRF            | electronic case report form                               |
| EDC             | electronic data capture                                   |
| ELISA           | enzyme-linked immunosorbent assay                         |
| EOS             | End of Study (visit)                                      |
| EOT             | End of Treatment (visit)                                  |
| EU              | European Union  |
| FDA             | United States Food and Drug Administration                |
| GCP             | Good Clinical Practice                                    |
| G-CSF           | granulocyte colony stimulating factor                     |
| GGT             | gamma glutamyl transferase                                |
| GI              | Gastrointestinal  |
| GLP             | Good Laboratory Practices                                 |
| GM-CSF          | granulocyte macrophage-colony stimulating factor          |
| GMP             | Good Manufacturing Practice                               |
| Hb              | Hemoglobin  |
| Het             | Hematocrit  |
| HDPE            | high-density polyethylene                                 |
| hERG            | human ether-à-go-go related gene                          |
| HIV             | human immunodeficiency virus                              |

CONFIDENTIAL This document is confidential. Do not disclose or use except as authorized. 8

| Abbreviation     | Term   |
|------------------|--|
| HNSTD            | highest nonseverely toxic dose   |
| IB               | Investigator's Brochure  |
| IC 50 | concentration producing 50% inhibition                                   |
| ICF              | informed consent form  |
| ICH              | International Conference on Harmonisation                                |
| IEC              | independent ethics committee   |
| IRB              | institutional review board   |
| ITT              | intent-to-treat  |
| IV               | intravenous; intravenously   |
| IVRS             | interactive voice response system  |
| K i   | inhibition constant  |
| KPS              | Karnofsky Performance Status   |
| LDH              | lactate dehydrogenase  |
| LFT              | liver function test(s)   |
| MedDRA           | Medical Dictionary for Regulatory Activities                             |
| Millennium       | Millennium Pharmaceuticals, Inc., and its affiliates                     |
| MRI              | magnetic resonance imaging   |
| MRU              | medical resource utilization   |
| MTD              | maximum tolerated dose   |
| MUGA             | multiple gated acquisition (scan)  |
| NCCN             | National Comprehensive Cancer Network                                    |
| NCI              | National Cancer Institute  |
| NCI CTCAE        | National Cancer Institute Common Terminology Criteria for Adverse Events |
| NPO              | nothing by mouth   |
| NYHA             | New York Heart Association   |
| PBMC             | peripheral blood mononuclear cell  |
| PCR              | polymerase chain reaction  |
| PD               | progressive disease (disease progression)                                |
| Pgp              | P-glycoprotein   |
| РК               | pharmacokinetic(s)   |
| РО               | per os ; by mouth (orally)  |
| PR               | partial response   |
| PRO              | patient-reported outcome   |
| PSA              | prostate-specific antigen  |
|                  |  |

CONFIDENTIAL This document is confidential. Do not disclose or use except as authorized. 9

| Abbreviation     | Term  |
|------------------|---|
| QD               | quaque die; each day; once daily                            |
| QID              | quater in die; 4 times a day                                |
| QOD              | quaque altera die; every other day                          |
| QOL              | quality of life   |
| QTc              | rate-corrected QT interval (millisec) of electrocardiograph |
| RBC              | red blood cell  |
| RECIST           | Response Evaluation Criteria in Solid Tumors                |
| SAE              | serious adverse event                                       |
| SC               | Subcutaneous  |
| SD               | stable disease  |
| SmPC             | Summary of Product Characteristics                          |
| $t_{1/2}$        | terminal disposition half-life                              |
| TGI              | tumor growth inhibition                                     |
| T max | single-dose time to reach maximum (peak) concentration      |
| UK               | United Kingdom  |
| ULN              | upper limit of the normal range                             |
| US               | United States   |
| Vz               | volume of distribution in the terminal phase                |
| WBC              | white blood cell  |
| WHO              | World Health Organization                                   |

## **PROTOCOL SUMMARY**

# Study Title: Phase II Trial of Combination of Ixazomib and Lenalidomide and Dexamethasone in Smoldering Multiple Myeloma

#### Phase: II

#### Number of Patients: 56

#### **Study Objectives:**

**Primary Objectives** 

- To determine the proportion of patients with high-risk smoldering multiple myeloma patients who are progression free at 2 years after receiving IRD combination therapy Secondary Objectives
  - To assess the response rate of the combination in these patients
  - To assess duration of response
  - To assess safety of the combination
  - To examine molecular evolution of the tumor cells
  - To determine minimal residual disease (MRD)
  - To assess time to progression and progression free survival

#### **Overview of Study Design:**

This is a single arm phase II study using the combination of Ixazomib and lenalidomide + dexamethasone in patients with high-risk smoldering multiple myeloma. The study is designed to examine novel therapeutic combinations in patients with smoldering MM. Based on the activity of lenalidomide and dexamethasone in patients with SMM and based on the safety and activity profile of Ixazomib/len/dex in patients with untreated MM, we propose to examine in a phase II trial the activity of ixazomib/lenalidomide/dexamethasone (IRD) in patients with high-risk smoldering MM.

#### **Study Population:**

SELECT INCLUSION CRITERIA

- Age  $\geq$  18 years.
- High-risk smoldering myeloma based on the new Rajkumar et al criteria for high-risk disease.
- No evidence of CRAB criteria or new criteria of overt MM which includes the following:
  - Increased calcium levels (corrected serum calcium >0.25 mmol/dL above the upper limit of normal or >.275 mmol/dL) related to MM
  - Renal insufficiency (attributable to MM)
  - Anemia (Hb 2g/dL below the lower limit of normal or <10g/dL) related to MM
  - Bone lesions (lytic lesions or generalized osteoporosis with compression fractures)
  - No evidence of the following new criteria for active MM including the following: Bone marrow plasma cells >60%, Serum involved/uninvolved FLC

ratio  $\geq 100$  (light chain smoldering MM is allowed), and MRI with more than one focal lesion.

- ECOG Performance Status (PS) 0, 1, or 2.
- The following laboratory values obtained  $\leq 21$  days prior to registration:
  - $\circ$  ANC  $\geq 1000/\mu L$
  - $\circ$  PLT  $\geq$  75,000/ $\mu$ L
  - Total bilirubin  $\leq$  1.5 mg/dL (If total is elevated check direct and if normal patient is eligible.)
  - AST  $\leq$  3 x institutional upper limit of normal (ULN)
  - ALT  $\leq$  3 x institutional upper limit of normal (ULN)
  - Calculated creatinine clearance  $\geq$  30 mL/min

#### SELECT EXCLUSION CRITERIA

- Symptomatic Multiple Myeloma or any evidence of CRAB criteria. Any prior therapy for Multiple Myeloma should also be excluded. Bisphosphonates are not excluded
- Other concurrent chemotherapy, immunotherapy, radiotherapy, or any ancillary therapy considered investigational. Prior therapy with bisphosphonate is allowed. Prior radiation therapy to a solitary plasmacytoma is allowed.

**Duration of Study:** 5 years

#### **1. OBJECTIVES**

Smoldering Multiple Myeloma (SMM) is a heterogeneous disease entity that includes patients who have a disease burden that is higher than that in patients with MGUS but who are not yet symptomatic. The term SMM was first described by Greipp and Kyle et al in 1980^3 and was followed by many other descriptions terming it indolent MM, or Durie Salmon Stage I. It was not until 2003 that the International Myeloma Working Group (IMWG) described the exact definition of this disease. SMM was defined as serum M-protein  $\geq 3$  g/dL and/or  $\geq 10\%$  monoclonal plasma cells in the bone marrow (BM), Table 1. While the incidence and prevalence of SMM in the population is not well defined, it has been estimated to represent approximately 8% to 20% of patients within the MM spectrum^2.

Most recently, the IMWG further re-defined the group of patients who meet criteria for treatment and included asymptomatic SMM patients who are likely going to have end-organ damage in the near future, previously defined as "ultra-high-risk smoldering myeloma". These include patients with bone marrow plasmacytosis  $\geq 60\%$  ; an abnormal FLC-ratio  $\geq 100$  (involved kappa) or < 0.01 (involved lambda) : and/or 2 or more focal bone marrow lesions detected by functional imaging including PET-CT and/or MRI . These patients should therefore not be considered SMM anymore but rather re-defined as patients with myeloma-defining events that require therapy.

The overall risk of progression of SMM is 10% per year for the first 5 years and 3% per year for the next 5 years. The most common factors used to stratify patients with SMM are the Mayo Clinic criteria and the Spanish PETHEMA criteria. The Mayo Clinic criteria are based on the tumor burden defined by the serum protein level (by serum protein electrophoresis or light chain ratio) or by the percent bone marrow plasma cell involvement (see Table 2 ), leading to risks of progression at 5 years of 25% for low risk, 51% for intermediate risk and 76% for high-risk individuals who have 1, 2 or 3 risk factors respectively. The risk stratification of the PETHEMA group is based on identifying the number of clonal plasma cells in the bone marrow by flow cytometry ( $\geq$  95% ratio of abnormal neoplastic plasma cells to normal plasma cells) and reduction of uninvolved immunoglobulins, with 5 year-risk of progression being 4%, 46%, and 72% for patients with 0, 1 or 2 risk factors, respectively.

The paradigm of therapy in Smoldering Multiple Myeloma (SMM) is changing as we develop better therapeutic agents that prevent end organ damage and improve survival of patients with multiple myeloma (MM). Indeed, recent studies of a phase III trial of lenalidomide and dexamethasone versus placebo showed improved response, progression free survival and overall survival in patients with high-risk smoldering MM compared to placebo control. Therefore, there is a need to examine novel therapeutic combinations in patients with high-risk smoldering MM. Based on the activity of lenalidomide and dexamethasone in patients with high-risk SMM and based on the safety and activity profile of Ixazomib and lenalidomide in patients with relapsed MM, we propose to examine the activity of Ixazomib, lenalidomide, and dexamethasone in patients with SMM.

Our overarching hypothesis is that early therapeutic interventions in patients with smoldering MM will prevent/delay progression to overt MM. We will examine the *in vivo* activity and safety of Ixazomib, lenalidomide, and dexamethasone in patients with high-risk SMM.

#### 1.1 Study Design

This is a phase II study using the combination of Ixazomib and lenalidomide + dexamethasone in patients with high-risk smoldering multiple myeloma.

#### **1.2** Overview of Study Design

This is a single arm phase II study using the combination of Ixazomib and lenalidomide + dexamethasone in patients with high-risk smoldering multiple myeloma.

The study is designed to examine novel therapeutic combinations in patients with smoldering MM. Based on the activity of lenalidomide and dexamethasone in patients with SMM and based on the safety and activity profile of Ixazomib/len/dex in patients with untreated MM, we propose to examine in a phase II trial the activity of ixazomib/lenalidomide/dexamethasone (IRD) in patients with high-risk smoldering MM, including those with all risk factors of SMM.

### **1.3** Number of Patients

A total of 56 patients will be included on this study. Enrollment includes patients who receive the first day of therapy. Patients who are registered, but never start protocol therapy should be replaced.

#### **1.4 Duration of Study**

A treatment cycle is defined as 28 consecutive days.

Patients will receive 9 cycles of induction therapy followed by 15 cycles of maintenance therapy for a total of 24 months.

For treatment cycles 1 and 2, a +/-3 day window is allowed. For treatment cycles 3 through 24, a +/-7 day window is allowed. Treatment plan is designed to be administered on an outpatient basis, however if necessary, may be given as inpatient.

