#### 5.3 General Concomitant Medication and Supportive Care Guidelines

5.3.1 Medications and supportive care

- Patients who experience worsening neuropathy from baseline may be observed for recovery, and have dose reductions/delays as indicated in the protocol, and any supportive therapy or intervention may be initiated as appropriate at the discretion of the investigator.
- Supportive measures consistent with optimal patient care may be given throughout the study.
- Stem cell mobilization will be allowed at the time of best response or at the end of induction therapy (after 9 cycles) for patients who are eligible for stem cell transplant. Standard mobilization treatment (with GCSF or with cyclophosphamide or plerixafor, etc) will be used based on Institutional guidelines. Patients may delay treatment for up to 6 to 8 weeks for mobilization purposes. Filgrastim is allowed per standard protocol for stem cell mobilization if stem cell mobilization will be performed. This will be allowed per standard procedure of stem cell collection per

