#### 6. DOSING DELAYS/DOSE MODIFICATIONS

#### 6.1 Recommended Ixazomib Criteria for Beginning or Delaying a Subsequent Treatment Cycle & Dose Modifications for Treatment Associated Toxicity

For a new cycle of treatment to begin during induction, the patient must meet the following criteria:

- ANC must be  $\geq 1,000/\mu$ L.
- Platelet count must be  $\geq 75,000/\mu$ L.
- All other clinically significant, study drug related non hematologic toxicity must have resolved to ≤ Grade 1 or to baseline condition

If the participant fails to meet the above-cited criteria for initiation of a new cycle of treatment during induction, dosing will be delayed for 1 week. At the end of that time, the participant should be re-evaluated to determine whether the above criteria have been met. If the participant continues to fail to meet the above-cited criteria, delay therapy and continue to re-evaluate. The maximum delay for toxicity before treatment is permanently discontinued will be 3 weeks, however delays due to other circumstances should be discussed with the Principal Investigator. Delays of > 3 weeks must be discussed with the Principal Investigator. Re-treatment will be at the discretion of the Principal Investigator.

During maintenance, the above pre-treatment criteria must only be met every 3 months during cycles when a provider is seen. During cycles when the patient does not return to clinic, sites must follow local guidelines for pre-treatment criteria.

There is no specific pre-treatment criteria for lenalidomide during induction or maintenance. Sites should follow local guidelines for beginning a new cycle of treatment with lenalidomide.

If any one of the study medications is permanently discontinued for toxicity, the patient may remain on the study at the discretion of the investigator.

| Dose Level    | Dose        |
|---------------|-------------|
| Starting Dose | 4.0 mg      |
| -1            | 3.0 mg      |
| -2            | 2.3 mg      |
| -3            | Discontinue |

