#### CONFIDENTIAL

This document is confidential. Do not disclose or use except as authorized.
12-A CD of scans at screening and end of treatment is required to be sent to the lead site for central review Screening scans should be sent with the eligibility packet to the lead site-This requirement includes a full body skeletal survey in addition to spinal MRI OR the patient may have only a low dose PET CT

Note: Research blood and bone marrow studies of all cycles after cycle 1 are voluntary and do not exclude patients from participating

13 – Participants unable to come in for follow up every 3 months can be allowed to come in every 6 months for follow up at PI discretion in accordance with standard of care follow-up frequency

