### 13.1.1 Analysis of Primary Endpoint

Time to progression (TTP) is defined as the time from protocol therapy initiation until documented progression, censored at date last known progression-free for those who have not progressed. At time of final analysis, the 2-year progression-free rate will be estimated using the Kaplan-Meier method with 95% confidence interval. All patients who have received one dose of study treatment will be included for the TTP analysis, including those who die or are lost to follow-up within 2 years.

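### No assessment is required at 24 months from the start of therapy, and 24 cycles of 28 days end at 22.1 months, so the 2-year progression-free rate may be biased upward by 0 to about 2.9 points

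*Combined protocol and SAP*

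**What the plan says.** Section 1.4 (Duration of Study) defines the cycle, "A treatment cycle is defined as 28 consecutive days", and then gives the whole course: "Patients will receive 9 cycles of induction therapy followed by 15 cycles of maintenance therapy for a total of 24 months". Section 5.1 repeats both statements.

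Section 13.1.1 times progression from the start of protocol therapy to its documentation. On the estimator it says "the 2-year progression-free rate will be estimated using the Kaplan-Meier method", with a 95% confidence interval. Section 13.1 compares the rate with 50%.

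The calendar in Section 10 has these visits around the landmark:
- in cycles 10-24, assessments every 3 months;
- an end-of-treatment visit with a window of 2 weeks either side, including marrow and imaging;
- event monitoring every 3 months, with the same window, covering examination, blood counts, chemistry, free light chains and electrophoresis, but neither marrow nor imaging.

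Footnote 13 relaxes monitoring at the investigator's discretion: "Participants unable to come in for follow up every 3 months can be allowed to come in every 6 months for follow up". No section states the date from which monitoring is counted, and none requires an assessment at 24 months from therapy initiation.

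**The concern.** The endpoint is a landmark rate, and a progression found at a visit takes the date of that visit. If the last look before the landmark is at about 22 months and the next at about 25, or 28 on the 6-monthly option, a progression arising in months 22 to 24 can be dated after 2 years. The patient then counts as progression-free at 2 years.

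The error goes one way, because late detection can only move an event date later. There is no control arm to share the delay: the estimate is set against a fixed 50%. Any bias therefore favours declaring the regimen effective.

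**Working it through.** **Plan's own design figures.** Inputs from Section 13.1: null 50%, alternative 70%, 53 eligible patients, stated probabilities of success 0.05 and 0.91. An exact one-sided binomial rule requiring at least 33 of 53 gives P(X >= 33 | 0.50) = 0.049 and P(X >= 33 | 0.70) = 0.914. The design reproduces, but the cut-off of 33 is inferred.

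**Duration.** 24 x 28 = 672 days; 672 / 30.4375 = 22.1 months. Two years is 730.5 days, so the shortfall is 58.5 days.

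**Visit windows, no delays, monitoring counted from end of treatment.**
- End of treatment: 672 +/- 14, that is days 658-686.
- First monitoring visit: 672 + 91.3 = day 763 (25.1 months), window days 749-777.
- Six-monthly option: 672 + 182.6 = day 855 (28.1 months).

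Day 730 lies in none of these windows.

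**Bias in the 2-year estimate.** Assume a constant hazard and no dropout. If every progression after day 672 waits for the next visit, the estimate at 2 years is really S(672) = S(730.5)^(672/730.5).
- True 50%: 0.50^0.9199 = 0.529, or +2.9 points.
- True 70%: 0.70^0.9199 = 0.720, or +2.0 points.

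The documents do not give the share of these progressions that would be documented between visits, so the full range is shown. The 33-of-53 rule stands in for the Kaplan-Meier analysis.

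| Share found only at the next visit | Estimate at true 50% | Type I error, 33/53 | Estimate at true 70% |
|---|---|---|---|
| none | 0.500 | 0.049 | 0.700 |
| half | 0.514 | 0.074 | 0.710 |
| all | 0.529 | 0.108 | 0.720 |

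**A stricter rule.** If success meant an exact two-sided 95% lower limit above 50%, at least 35 of 53 would be needed, since P(X >= 34 | 0.50) = 0.027 and P(X >= 35 | 0.50) = 0.014. With all progressions in the gap found late, P(X >= 35 | 0.529) = 0.036.

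**How much is due to the 58 days?** Simulating end of treatment at 24 calendar months +/- 2 weeks still leaves about +2.0 to +2.3 points at a true 50%, depending on the visit grid assumed. Visits in the later half of the window are dated after the landmark, and the preceding visit is months earlier. Correcting the duration alone therefore removes little. For the same reason, counting monitoring from cycle 1 day 1 without a dating rule still leaves about +1.5 points in simulation.

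**Check of the proposed rule.** If every event-free patient is seen at 730.5 +/- 14 days and a progression found there counts as an event by 2 years, the mean of 0.50^(t/730.5) over t from 716.5 to 744.5 is 0.500. The visit-detection bias disappears.

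**The case against.** A reader might infer that nobody is assessed at 2 years and that the primary result is therefore biased. The documents do not support that.
- The monitoring anchor is unstated. Counted from cycle 1 day 1, a visit falls at month 24.
- Delays move the grid. Section 1.4 says "For treatment cycles 3 through 24, a +/-7 day window is allowed", Section 6.1 says "The maximum delay for toxicity before treatment is permanently discontinued will be 3 weeks", and Section 5.3.1 says "Patients may delay treatment for up to 6 to 8 weeks for mobilization purposes". An accumulated delay of about 6 to 10 weeks (730.5 - 686 = 44.5 days to 730.5 - 658 = 72.5 days) puts the end-of-treatment window over 2 years. Patients who stop early follow another grid.
- Kaplan-Meier needs no visit on the landmark day, and follow-up continues well past it. Symptomatic progressions can be documented between visits; if all are, the bias is zero.
- The maximum of 2 to 3 points is small beside a 95% half-width of about 12 to 13 points at n = 53. Section 13.1 also derives its 50% from a 1.9-year median. Under that hazard, survival at day 672 is 51.1%, and the 33-of-53 rule succeeds with probability 0.068.
- Treatment length is clear in practice, because the regimen is laid out by cycle number.

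All of this limits the size and generality of the point, and it stands. What remains is that nothing in the plan secures an assessment at the landmark, and that the error can go only one way.

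A reader might also see a conflict between the schema's note, "Disease Assessment: Day 1 of each cycle", and the 3-monthly maintenance column. That is not supported. The figure to which the note belongs is not shown, so its scope is unknown, and Section 5.1 expressly allows visits every third cycle in maintenance.

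**Conclusion.** The point holds in a limited form. The contradiction between 24 cycles of 28 days and 24 months is certain. So is the absence of both a stated monitoring anchor and a required 24-month assessment. The bias is conditional: 0 to 2.9 points at a true 50%, and 0 to 2.0 at 70%. It applies to patients on schedule whose monitoring is counted from end of treatment.

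A type I error of up to 0.108 is a worst case under an inferred rule. It should not be read as the trial's actual error rate, since the plan states no cut-off. The figures assume a constant hazard, no dropout, and a binomial rule in place of the Kaplan-Meier analysis. The main cause is visit spacing combined with dating by detection; the shortfall in days is secondary. The change is worth making because it is cheap and removes a one-sided error against a fixed benchmark.

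**What to change.** 1. In Sections 1.4 and 5.1, reconcile the 24-month duration with 24 cycles of 28 days. This review takes no position on which is intended.
2. In the Section 10 calendar, state the date from which event monitoring is counted. Keep the existing 3-monthly visits, but align one of them to 24 months (+/- 2 weeks) from cycle 1 day 1 for every event-free patient, on or off therapy. The 6-monthly option should not apply to that visit. Aligning one visit, rather than fixing the first monitoring visit at 24 months, avoids postponing monitoring for patients who stop early.
3. In Section 13.1.1, state that a progression found at the 24-month visit, within its window, counts as an event by 2 years. Add an interval-censored sensitivity analysis of the 2-year rate. Counting every event found at the next visit as a 2-year event would over-correct on the present schedule: at a true 50% it gives 0.50^(763.3/730.5) = 48.5%, or 0.50^(854.6/730.5) = 44.4% on the 6-monthly option.

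The cost is calendar and analysis wording, a little analysis work, and one fixed visit for patients on the 6-monthly option or those who stopped early and are off that grid. One limitation remains and should be stated: event monitoring includes neither marrow nor imaging, so progressions defined by those tests would still be found only when clinically prompted.
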